APPENDIX II ADVERSE EVENT GRADING

Adapted DAIDs score for neonates, reproduced from the IMPAACT study.³⁸

Parameter	Grade 0 Normal	Grade 1 Mild	Grade 2 Moderate	Grade 3 Severe	Grade 4 Potentially Life-Threatening
Apnea* *Apnea spell defined as apnea event >20s or associated with bradycardia, hypoxia or cyanosis	No apneas	< 6 spells* per day	6<12 spells* per day or nasal cannula for apnea	12 or more spells* per day or nasal continuous positive airway pressure (NCPAP) for apnea	Requires intubation for apnea
Anemia	Hb > 10	Hgb 8-10 g/dL	Hgb ≤ 8 g/dL	Requires packed red cell transfusion, no clinical signs	Requires packed red cell transfusion, clinical signs of shock
Congenital Anomalies	None	Minor (no impairment of function)	Minor (no impairment of function), future treatment may be needed	Major (impairment of function), no immediate treatment needed	Major (impairment of function), immediate treatment needed
Congenital Heart Disease	No congenital heart disease	Minor (no impairment of function), no treatment needed	Minor (no impairment of function), future treatment may be needed	Major (impairment of function), no immediate treatment needed	Major (impairment of function), immediate treatment needed
Elecotrolyte/ Metabolic Disorders	None		Electrolyte/Metabolic disorder, no systemic signs		Electrolyte/Metabolic disorder with systemic signs
GI dysfunction [including necrotizing entercolitis(NEC)]	None	Not ill, abnormal abdominal exam, no treatment needed (e.g., abdominal distension but not NPO)	Mild illness, NPO <3 days (e.g., R/O necrotizing entercolitis (NEC) evaluation, Stage I NEC)	Moderate illness, NPO 3-7 days, or medical treatment (e.g., Stage II NEC)	Severe illness, NPO>7 days, or surgical treatment needed (e.g., Stage III NEC)
Hypertension	No BP performed	Systolic BP> 80- 100, no treatment	Systemic BP > 100, no treatment	Treated with one agent	Treatment with multiple agents
Hypotension	No BP performed	Mild clinical signs, no treatment needed	Symptomatic, treated with IV fluids	Symptomatic, treated with single medication	Clinical signs of shock or requiring use of multiple medications
Intraventricular Hemmorhage	No abnormality noted or not assessed	Germinal matrix hemorrhage	Blood in ventricle, no enlargement	Blood in ventricle, with ventricular enlargement	Parenchymal hemorrhage and/or need for ventricular drainage
Jaundice	No jaundice	Mild jaundice, no treatment	Phototherapy and/or IVIG	Exchange transfusion	Acute bilirubin encephalopathy
Neonatal Abstinence Syndrome (NAS)	No history of abstinence syndrome	NAS signs, no medical treatment	NAS controlled with single drug	NAS controlled with two drugs	NAS with seizures
Neurologic compromise	Normal neurologica l examinatio ns	Mildly abnormal neurologic exam, no clinical or EEG seizure activity	Stage I encephalopathy or possible clinical or EEG seizure activity but no treatment	Stage II encephalopathy or single drug seizure therapy	Stage III encephalopathy or multiple drug seizure therapy
Neutropenia	ANC> 1000/mm3	ANC<1000/mm	ANC<500/mm ³	Treated with GCSF	WBC transfusion
Patent Ductus Arteriosus	No murmur	Clinical signs, no treatment	Treatment with fluid restriction or diuretics	Treatment with indomethacin or ibuprofen	Surgical ligation
Persistent Pulmonary Hypertension	No difference in pre- and	Supplemental O ₂ but no mechanical ventilation	Conventional ventilator < 5 days	Conventional ventilation 5-10 days, alternative ventilation (e.g., high frequency	Mechanical ventilation > 10 days

NeoCHG Protocol v2.0 29-Nov-2021

Parameter	Grade 0 Normal	Grade 1 Mild	Grade 2 Moderate	Grade 3 Severe	Grade 4 Potentially Life-Threatening
	post-ductal difference			oscillatory ventilation (HFOV), sildenafil and/or nitric oxide	
Renal Dysfunction	Wet diapers documente d	Urine output 1 < 1.5 mL/kg/hr	Urine output 0.5 <1.0 mL/kg/hr	Urine output 0 < 0.5 mL/kg/hr	Prolonged anuria
Respiratory Insufficiency	Baby is in room air – no supplement al oxygen	Nasal cannula oxygen with FiO2 <0.5	Continuous positive airway pressure (CPAP) or nasal cannula with FiO2>0.5	Conventional ventilation	Alternative ventilation (e.g., HFOV)
Retinopathy of Prematurity (ROP)	Normal vascularizati on or not assessed	Incomplete vascularization	Pre-threshold ROP	Threshold ROP or ROP treatment	Retinal detachment
Sepsis	No sepsis symptoms and signs	Septic evaluation, no treatment	R/O sepsis, antibiotics for ≤72 hours	A confirmed blood stream infection with a course of antibiotic treatment, no septic shock or meningitis	A confirmed blood stream infection with a course of antibiotic treatment with septic shock or meningitis
Thrombocytopenia	>100 000	75,000-100,000	50,000< 75,000	25,000<50,000	< 25,000 or platelet transfusion

REFERENCES

- 1. Seale, A. C. *et al.* Neonatal severe bacterial infection impairment estimates in South Asia, sub-Saharan Africa, and Latin America for 2010. *Pediatr. Res.* **74**, 73–85 (2013).

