6.7 FOLLOW-UP

Follow up will be until 28 days after randomisation, which will be via phone call if the baby has already been discharged. At day 28 the baby's vital status will be ascertained, together with occurrence of serious adverse events (including clinically defined sepsis, necrotising enterocolitis (NEC)) and any unscheduled visits to healthcare providers. Parents/carers will be provided with the trial team's details at discharge and will be told to bring their baby back to the hospital if they have any concerns.

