7.3.2 SEVERITY OR GRADING OF ADVERSE EVENTS

AEs, serious or not serious, should be graded using the Adapted DAIDS score for neonates, reproduced from the IMPAACT network³⁸ (Appendix II).

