The effect of each treatment arm will be assessed within a single model with each factor being fitted independently as a factor, and not as a continuous variable. Comparison of main effects within arms will be assessed using the estimate and 95% confidence interval of the comparison of differences between factors and in comparison, to control. As this is a pilot trial, the sample size was not powered to robustly detect interactions between chlorhexidine concentrations/frequencies and emollients and so we will not test these formally, but will use exploratory analyses to assess whether there is any evidence supporting individual interactions testing each one, one at a time. As this is a pilot trial and the two co-primary outcomes capture different aspects (efficacy and safety) there will be no adjustment for multiple testing, nor for the two different bacterial load outcomes since we expect a reduction in colonisation on the skin, but potentially no change in colonisation peri-rectally.

Similar mixed models will be used to analyse change in skin temperature after vs before each application, including individual as a random effect, the change in temperature as the outcome and the pre-application (baseline) temperature as a factor. Acquisition and loss of each species will be analysed as a binary outcome variable, compared with baseline, in the relevant population (those without the species of interest at baseline, or with the species of interest at baseline, respectively).

Presence/absence of each species at each assessment will also be compared between randomised groups using mixed models, again with individual as a random effect, and with baseline presence as a factor.

Frequency of SAEs will be tabulated by randomised group, and compared using exact logistic models (or time-to-event models if AEs occur in >10% of the trial population overall). SAEs will also be tabulated by grade. Similar analyses will be conducted for the AEs in Appendix II.

A Statistical Analysis Plan will be written and approved by the Trial Management Group (TMG) and the DMC before the first interim analysis is reviewed by the DMC.

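### The Sepsis row of Appendix II has no grade for sepsis treated beyond 72 hours without a confirmed bloodstream infection, so these episodes cannot be validly graded or tabulated by grade

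*Protocol*

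**What the plan says.** The Sepsis row of the protocol's Appendix II starts at Grade 0 for a baby without symptoms or signs. The remaining grades are:

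- Grade 1: "Septic evaluation, no treatment"
- Grade 2: "R/O sepsis, antibiotics for ≤72 hours"
- Grade 3: "A confirmed blood stream infection with a course of antibiotic treatment, no septic shock or meningitis"
- Grade 4: "A confirmed blood stream infection with a course of antibiotic treatment with septic shock or meningitis"

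Three other parts of the protocol rely on this row.

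- **Grading.** Section 7.3.2 states that "AEs, serious or not serious, should be graded using the Adapted DAIDS score for neonates". Section 7.1.2 gives the task to the investigator at each scheduled visit.
- **Ascertainment.** Section 6.7 asks at day 28 for "occurrence of serious adverse events (including clinically defined sepsis, necrotising enterocolitis (NEC", and the footnote to the Trial Assessment Schedule says the same. Clinically defined sepsis is thus an event the trial sets out to collect, without any requirement for a positive culture.
- **Analysis.** Section 9.5 says "Frequency of SAEs will be tabulated by randomised group, and compared using exact logistic models", or time-to-event models if events are common. It adds that "SAEs will also be tabulated by grade" and plans similar analyses for the Appendix II adverse events.

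**The concern.** The row changes its criterion part-way up. Grades 1 and 2 are separated by treatment and its length. Grades 3 and 4 are reached only through a confirmed bloodstream infection. An episode that exceeds the length limit of Grade 2 but has no confirmed infection is left with nowhere to go.

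A site facing such an episode has three options, none of them valid:

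- leave the grade blank;
- record Grade 2, although treatment ran past its limit;
- record Grade 3 or 4, although no infection was confirmed.

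The choice is made by staff who know the allocation (sections 4.2 and 5.4), in two hospitals whose culture practice may differ.

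The event is not a marginal one here. Section 10.2.1 gives skin damage that could lead to infection as the main ethical concern, and section 1.4.6 says the larger trial that this pilot serves would have neonatal sepsis as its primary endpoint. Severity of sepsis by regimen is something that readers of the pilot will look for.

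**Working it through.** The protocol gives no figure to reproduce, and no power or sample-size quantity is involved. The check is whether the Sepsis row covers all cases.

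**Step 1. Cross the row's own criteria:** antibiotic treatment, confirmation of bloodstream infection, and septic shock or meningitis.

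| Antibiotics | Bloodstream infection confirmed | Shock or meningitis | Grade available |
|---|---|---|---|
| None, evaluated only | No | No | 1 |
| 72 hours or less | No | No | 2 |
| 72 hours or less | No | Yes | No Grade 3 or 4; only the duration limit of Grade 2 fits |
| More than 72 hours | No | No | None |
| More than 72 hours | No | Yes | None |
| A treatment course | Yes | No | 3 |
| A treatment course | Yes | Yes | 4 |

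Two cells have no grade. In a third, the only fitting grade ignores the shock or meningitis. Milder unconfirmed episodes are covered by Grades 1 and 2.

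**Step 2. Look for a rule elsewhere.** Sections 6.7, 7.1.2, 7.2, 7.3.2 and 9.5 give none for these cells. The gastrointestinal row of the same appendix shows that the scale can do without such a gap: it moves from under 3 days, to 3-7 days, to over 7 days without feeds, or by treatment and stage, and needs no laboratory confirmation.

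**Step 3. Set the gap against each planned use.**

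- Grading by the investigator (7.1.2, 7.3.2): undefined for these episodes.
- Tabulation of serious events by grade (9.5), and any part of the Appendix II analyses that uses grade: undefined for these episodes.
- Comparison of serious-event frequency between arms (9.5): needs only occurrence, so it can be done.
- Reporting of serious events to the trials unit within 24 hours (7.2, 7.3.1): rests on the seriousness criteria, not on grade.
- Weekly serious-event reports to the DMC (9.4): do not depend on grade.
- Co-primary outcomes (9.2.1) and sample size (9.3): do not use this scale.

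**Step 4. Ask whether the grade could be rebuilt at analysis.** Section 5.7 records all antibiotics, so long courses can be found. Blood-culture status is not among the data items named in the Trial Assessment Schedule, section 5.7 or section 6.1. Section 7.3.5 says only that copies of test results may accompany a serious-event form. Later repair is therefore uncertain.

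**The case against.** The strongest reply is that little depends on the grade. The planned between-arm comparison uses frequency, seriousness is judged separately, and a serious culture-negative episode is still reported, reviewed and counted. This is correct, and it confines the point to grading and tables by grade. A reader might infer that clinically defined sepsis cannot be compared between arms at all. Section 9.5 does not support that.

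Second, severe illness may appear in other rows. Signs of shock reach Hypotension Grade 4, and seizures, encephalopathy, ventilation or intubation for apnoea are graded under their own headings. This stands, so the baby does not vanish from the severity tables. But the illness is then not graded as sepsis.

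Third, a reader might infer that severe sepsis would be understated. The three options open to a site do not all point that way: a blank or Grade 2 lowers the severe count, while Grade 3 or 4 raises the count of apparently confirmed infection. Blanks may also be queried under the central checks of section 8.2, although a query cannot supply a grade that does not exist. The direction of error is not established.

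Fourth, the scale is reproduced from an existing network and was chosen because earlier neonatal trials used it. That explains the wording but does not close the gap, because this protocol makes the scale its own rule and also collects clinically defined sepsis.

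**Conclusion.** The point holds as a defect in a stated rule. Sepsis treated for more than 72 hours without a confirmed bloodstream infection has no grade, with or without septic shock or meningitis, although the protocol requires one and plans to tabulate by it. This is not a detail that a statistical analysis plan could settle alone, because the grade is assigned at the site from Appendix II and the culture result needed to reassign it may not be in the database.

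The consequence is modest. Serious adverse events are a secondary outcome, and the co-primary outcomes, the power, the frequency comparison and the DMC's serious-event reports are untouched.

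The number of babies concerned cannot be taken from the documents, which give neither a sepsis incidence nor a culture yield. If one simply assumed that 15-30% of the 182 babies were treated beyond 72 hours and that 60-90% of those were unconfirmed, the result would run from 182 × 0.15 × 0.60 ≈ 16 to 182 × 0.30 × 0.90 ≈ 49. A reader should not take this as an estimate. Both ranges are assumptions, and the sum counts every long course as a new trial event, whereas section 7.1.4 excludes pre-existing conditions that do not worsen. The conclusion rests on the wording of the row and not on any such count.

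**What to change.** Amend the Sepsis row so that the grades leave no gap. This changes how events are classified, not how babies are treated. One workable form:

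- Grade 3: sepsis treated with antibiotics for more than 72 hours, whether culture-confirmed or clinically defined, without septic shock or meningitis.
- Grade 4: sepsis with septic shock or meningitis, whatever the culture result.

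Add one CRF field for culture status (positive, negative, not taken), and tabulate Grade 3-4 sepsis by that field. Confirmed infection can then still be reported alone, and the grade on the source scale can be rebuilt wherever that scale has one.

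The cost is one row, one field and site notification. There are two small downsides. The row no longer matches the source scale word for word. Grade 3 would also partly reflect each hospital's practice on length of antibiotic treatment, so that a stable baby on a long precautionary course would sit beside a confirmed infection. The culture field and the antibiotic records already required by section 5.7 make both visible in the tables.
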